4. STUDY DESIGN

This is an observational longitudinal cohort study. Two separate patient cohorts will be considered:

1. Those approached for consent at time of transplant: baseline, 6 weeks post-transplant and 1-year post transplant measurements will be obtained
2. Those approached for consent at time of wait-listing: baseline values at time of wait-listing, time of transplant, 6 weeks and 1 year post transplant will be obtained.

5. STUDY SETTING

The study will be conducted within the West of Scotland Renal Transplant Unit and NHS Greater Glasgow and Clyde Urology. This is a high-volume tertiary center with a dedicated renal transplant program catering to entire Scotland. This center works in close association with Urology and Nephrology departments making it an ideal site for conducting a multidisciplinary longitudinal study.

6. PARTICIPANT ELIGIBILITY CRITERIA

Inclusion criteria

All adult patients (≥ 18 years old) scheduled to undergo first time renal transplantation (both deceased and living donor candidates).

Exclusion criteria

- Unable or unwilling to provide consent
- Patients undergoing re-transplant (to avoid confounding because of previous interventions)
- Patients undergoing simultaneous urological reconstructive procedures
- Patients with previously reconstructed bladders (includes Augmentation cystoplasty, ileal conduit, neobladder etc.)
- Significant cognitive impairment which would limit their capacity to accurately report symptoms

In line with NIHR guidance on equality, diversity and inclusion all people regardless of gender, sexual orientation, pregnancy, ethnicity, religion and socioeconomic status will be offered the same opportunity to participate. Hospital translators will be used where appropriate to obtain consent and the HR-QoL tools employed are available in a large variety of languages. Where it may not be possible to provide a translated HR-QoL tool, this will not serve as a contraindication to participation should the patient wish to, rather this secondary outcome measure will be omitted from data collection.

Both for equity and for scientific integrity, it's important that roughly equal numbers of men and women complete the study (as men will complete an IPSS and woman a ICIQ-FLUTS). Recruitment will be reviewed after 70 patients and patients targeted based on gender to ensure a fairly equal number of male and female participants.

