Sponsor's Representative	[name] Admin Building, Level 2 Administration building Gartnavel Royal Hospital [name] Glasgow [contact] Email: [contact]
Sponsor	NHS Greater Glasgow and Clyde
Funder(s)	XXXXXXX
Key Protocol Contributors	[name] [name], Urology Research Fellow, Glasgow [name], Consultant Urologist, Glasgow [name], Statistician, Glasgow [name], Consultant Transplant Surgeons, Glasgow

SCIENTIFIC SUMMARY

Research questions:

1. What is prevalence and distribution of lower urinary tract symptoms (LUTS) in the renal transplant population?
2. Is there an association between pre-transplant LUTS scores and urological adverse outcomes following transplantation?

Background:

Urological consultation is an essential step in the pre-operative workup for patients before placing them on a waiting list for a renal transplant. The aim of this workup is to diagnose, treat and optimize any pre-existing urological pathology to maximize post-transplant graft function. Pre-existing lower urinary tract symptoms (LUTS) are common in patients with end stage renal disease (ESRD). Similarly, post-transplant urinary tract infection (UTI) is the most encountered complication. The European Association of Urology (EAU) recommends comprehensive lower urinary tract evaluation of patients prior to renal transplant. However the evidence on which these recommendations are based is limited and there is no standardized pathway followed across centers globally.

Aims and Objectives:

1. Primary objectives:

- a. To understand the distribution of LUTS score in patients undergoing renal transplantation
- b. To describe the distribution of LUTS scores across adverse outcomes post-transplant

2. Secondary objectives:

- To determine if there is a difference in distribution of LUTS scores between male and female patients
- To assess whether the presence of moderate to severe LUTS predict the occurrence of post-transplant significant urological complications in the 6 weeks and 12 months following transplantation.
- To evaluate whether the presence of moderate-severe LUTS can predict graft outcomes in the 12 months following transplantation
- To determine if duration of time on the transplant waiting-list and/ or RRT vintage and/or anuria predict objective change in LUTS or adverse urological outcomes post-transplant

- To determine if pre-existing urological conditions increase the likelihood of major urological complication following transplant

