7. TRIAL PROCEDURES

This is a prospective, single center, longitudinal cohort study. Two separate patient cohorts will be considered:

3. Those approached for consent at time of transplant: baseline, 6 weeks post-transplant and 1-year post transplant measurements will be obtained
4. Those approached for consent at time of wait-listing: baseline values at time of wait-listing, time of transplant, 6 weeks and 1 year post transplant will be obtained.

Patients will be recruited over a two-year period and followed-up until they are one year post-transplant; removed from the transplant waiting list or have died.

We aim to approach all patients at the time of transplant and at the time of transplant wait-listing to offer participation.

This is primarily an observational study. History, examination and all perioperative follow-up will be conducted as would be standard of care. No additional hospital visits are required as the transplant assessment visit, transplantation, 6 week and 12 month follow-up visits will all coincide with regular clinical care.

Recruitment

Participant identification

Participants will be identified by a member of the clinical team either at time of referral for transplantation or at the time an offer of a kidney transplant offer is made. A member of the research team will be contacted and the patient screened for eligibility.

Screening

Case note review of patients' past medical and vascular access history will be undertaken by the research team to determine if eligibility criteria are met. If eligibility criteria are met, a PIS will be provided and the patient offered the opportunity to discuss the study further with the research team.

If a patient is screened but is not eligible for the trial, an anonymous record of the case will be kept in the screening log. The screening log will collect patient initials, age, and gender, date of screen failure and reason for screen failure. The screening log will be kept in the ISF.

Consent

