We aim to describe both IPSS (male) and ICIQ-FLUTS (female) in combination and separately. We would therefore hope to achieve roughly similar numbers of males and females recruited into the study. We'd therefore aim to evaluate recruitment after 70 patients and if gender distribution were unequal, target as required.

We anticipate it should be large enough to allow for 5-10% death rate (as would be standard in the transplant population). We do not anticipate that patients will be lost to follow-up as they all come back to regular post-transplant clinics but assuming 5-10% withdraw or have incomplete data sets. This is primarily an exploratory study. Little data exists about the prevalence of LUTS in renal/kidney transplant recipients. It is anticipated that the results of this study will inform sample size calculations for future interventional studies.

Data collection

All data will be collected within a password protected Microsoft Excel spreadsheet stored on an NHS-password protected computer. No patient identifiable information will be included within that spreadsheet only unique patient identifiers.

Data analysis

Data analysis will be exploratory with the primary aims of describing the distribution of LUTS scores for males and females and determining the prevalence of urological complications. These factors could inform sample size calculation, determine the correct primary endpoint for a future interventional study.

If appropriate, we may/ may not attempt to:

- Investigate the relationship between LUTS severity and urological complications
- Describe any change in LUTS whilst on the transplant waiting list/ post-transplant
- Establish a risk model for urological complications post-transplant.

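### If recruitment is targeted by sex, a crude pooled LUTS or complication prevalence may not describe the unit's transplant population; weight it and record the sex of all eligible patients

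*Protocol*

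**What the plan says.** The first research question in the Scientific Summary is "What is prevalence and distribution of lower urinary tract symptoms (LUTS) in the renal transplant population".

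On recruitment, section 7 states: "We aim to approach all patients at the time of transplant and at the time of transplant wait-listing". Section 6 adds that people are to have equal access to the study whatever their gender. The same section then says "Recruitment will be reviewed after 70 patients", with "patients targeted based on gender to ensure a fairly equal number of male and female participants". Its reason is that men complete the IPSS and women the ICIQ-FLUTS. Section 8 repeats the review but makes the action conditional: "if gender distribution were unequal, target as required".

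On reporting, section 8 says "We aim to describe both IPSS (male) and ICIQ-FLUTS (female) in combination and separately". Its data analysis paragraph gives the primary aims as "describing the distribution of LUTS scores for males and females and determining the prevalence of urological complications". The LUTS part of that aim is by sex. The complication part is a single prevalence, with no split by sex and no weighting mentioned.

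On records, section 7 (Screening) specifies a log entry, including gender, for patients screened and found ineligible. Section 7 (Consent) adds an entry for those who decline. Nothing describes an entry for an eligible patient who is not approached.

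**The concern.** Targeting is triggered only when the natural mix is unequal. Whenever it is used, it therefore moves the sample's sex mix away from that of the patients being transplanted or listed. A crude pooled proportion from such a sample averages men and women in quota proportions, while the research question asks about the population.

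Section 8 says the results could inform sample size and endpoint choice for a later interventional study, which need not recruit equal numbers of men and women. A pooled complication prevalence carried forward without adjustment could then be somewhat off. More patients would not cure this, and the confidence interval would not show it.

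There is also a practical gap. Correcting a pooled figure needs the sex mix of all eligible patients. If that is not recorded during recruitment, a later analysis plan cannot supply it unless unit records can.

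**Working it through.** **Inputs from the protocol (section 8).** 100 patients per part; 5-10% deaths; 5-10% withdrawals or incomplete data; at least 40 men and 40 women with complete data; expected composite complication prevalence 50-60%, not given by sex.

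**Assumed, because the protocol gives neither.** True male share π of 55-70%; male-minus-female difference in prevalence, D, of 0-30 points.

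**1. The protocol's own figure.** At the worst stated rates, 100 × (1 − 0.10 − 0.10) = 80, or 100 × 0.90 × 0.90 = 81. Split equally, that is 40 to 40.5 per sex, so 40 and 40 reproduces for a part of 100. It depends on balance: without targeting, a 65% male share would leave 80 × 0.35 = 28 women.

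**2. How strong the steering could be.** The text does not say whether 70 is per part or overall. Suppose the first 70 are 65% male, giving 70 × 0.35 = 24.5 women.
- Per part: reaching 50 of 100 needs 25.5 women among the last 30, or 85%.
- Overall: reaching 100 of 200 needs 75.5 women among the last 130, or 58%.

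**3. Distortion of a crude pooled prevalence.** With sample male share s, crude minus true = (s − π) × D. At full balance, s = 0.50. Absolute size in percentage points:

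| True male share π | D = 0 | D = 10 | D = 20 | D = 30 |
|---|---|---|---|---|
| 55% | 0 | 0.5 | 1.0 | 1.5 |
| 60% | 0 | 1.0 | 2.0 | 3.0 |
| 65% | 0 | 1.5 | 3.0 | 4.5 |
| 70% | 0 | 2.0 | 4.0 | 6.0 |

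Partial balance shrinks it: with π = 65%, s = 55% and D = 30, it is 0.10 × 30 = 3.0 points instead of 4.5.

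**4. Sampling error for comparison.** The half-width is 1.96 × √(p(1 − p)/n). At p = 0.55 it is 9.8 points for n = 100 and 10.9 for n = 80.

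**5. Price of weighting.** The weighted estimate is π × p(men) + (1 − π) × p(women). With 40 of each sex and p = 0.55 in both, its half-width is 1.96 × √((π² + (1 − π)²) × 0.55 × 0.45/40):
- π = 50%: 10.9 points
- π = 60%: 11.1 points
- π = 65%: 11.4 points
- π = 70%: 11.7 points

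Weighting removes the distortion, provided the recruited men and women each represent eligible patients of their sex.

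**The case against.** The protocol nowhere says that a pooled prevalence will be unweighted, and weighting is the kind of detail an analysis plan not shown here may hold. The balance is deliberate and useful: it secures enough women for a separate description, and it leaves sex-specific results undistorted. The main LUTS aim is already stated by sex. The text promises only fairly equal numbers, so the correction may be partial, and the distortion is smaller than the sampling error throughout the assumed range. All of this stands, and it keeps the point minor.

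Four stronger readings are tempting, and the document does not support them.
- That the pooled figures will be wrong. This needs targeting to be used, an unequal source mix and a sex difference in rates; the protocol establishes none of these.
- That the plan to combine covers complications. The sentence concerns the two LUTS instruments; the complication point rests only on the separately stated aim of a single prevalence.
- That using different questionnaires shows the protocol expects different rates. It does not: whether LUTS distributions differ by sex is listed as a secondary objective, so it is left open.
- That the screening log already holds the weights. As described, it covers ineligible patients and decliners, not eligible patients passed over once targeting starts.

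What an analysis plan could not settle is the recruitment text itself: whom to approach once targeting begins, and whose sex is recorded.

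**Conclusion.** The point holds in conditional form and is a minor improvement. If targeting is used and rates differ by sex, a crude pooled prevalence of complications or LUTS is a roughly 50:50 average and may not describe the unit's population. Under an assumed male share of 60-65% and a sex difference of 10-30 points, the distortion at full balance is 1.0-4.5 points; widening the share to 55-70% gives 0.5-6.0. It is zero if the source mix is equal or the rates do not differ. It stays below the sampling half-width of about 10-11 points but adds to it unseen.

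Separately, the aim of approaching everyone and the commitment to equal access regardless of gender are not reconciled with targeting by gender. That holds whatever the rates turn out to be.

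For LUTS, weighting solves only part of the problem. Section 20-point, 12-point and 16-point ICIQ-FLUTS subscales are summed against a cutoff that section 7 itself calls unofficial (12 or more for moderate), while men are classed by an IPSS above 7. A combined LUTS prevalence therefore mixes definitions that are not equivalent, whatever the sex mix.

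**What to change.** Keep the sex targeting, and make these changes.

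1. In section 8, name LUTS and composite-complication prevalence by sex as the main results.
2. Give any overall complication prevalence as the sex-specific estimates weighted to the sex mix of all eligible first transplants at the unit during recruitment (or all eligible listings, for the wait-listing part). Treat any combined LUTS prevalence the same way, with a note that the male and female instruments and cutoffs are not equivalent.
3. In section 7, extend the screening log to the sex of every eligible patient, including those not approached once targeting starts, or state that the counts will come from unit records.
4. Reconcile the statements on approaching all patients (section 7) and equal opportunity (section 6) with targeting by gender, and say whether the review at 70 applies to each part or to the whole study.

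The cost is a few sentences, one small addition to the log, and a slightly wider interval for the pooled figure: from 10.9 to between 11.1 and 11.7 points at 80 completers, for a male share of 60-70%. The sex-specific results are less precise than any pooled one: with 40 per sex and p = 0.55, 1.96 × √(0.55 × 0.45/40) gives about 15.4 points. That follows from the design and not from this change.

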7. TRIAL PROCEDURES

This is a prospective, single center, longitudinal cohort study. Two separate patient cohorts will be considered:

3. Those approached for consent at time of transplant: baseline, 6 weeks post-transplant and 1-year post transplant measurements will be obtained
4. Those approached for consent at time of wait-listing: baseline values at time of wait-listing, time of transplant, 6 weeks and 1 year post transplant will be obtained.

Patients will be recruited over a two-year period and followed-up until they are one year post-transplant; removed from the transplant waiting list or have died.

We aim to approach all patients at the time of transplant and at the time of transplant wait-listing to offer participation.

This is primarily an observational study. History, examination and all perioperative follow-up will be conducted as would be standard of care. No additional hospital visits are required as the transplant assessment visit, transplantation, 6 week and 12 month follow-up visits will all coincide with regular clinical care.

Recruitment

Participant identification

Participants will be identified by a member of the clinical team either at time of referral for transplantation or at the time an offer of a kidney transplant offer is made. A member of the research team will be contacted and the patient screened for eligibility.

Screening

Case note review of patients' past medical and vascular access history will be undertaken by the research team to determine if eligibility criteria are met. If eligibility criteria are met, a PIS will be provided and the patient offered the opportunity to discuss the study further with the research team.

If a patient is screened but is not eligible for the trial, an anonymous record of the case will be kept in the screening log. The screening log will collect patient initials, age, and gender, date of screen failure and reason for screen failure. The screening log will be kept in the ISF.

Consent

The Principal Investigator (PI) will retain overall responsibility for the conduct of research at their site, which includes the taking of informed consent of participants. They must ensure that any person delegated responsibility to participate in the informed consent process is duly authorised, trained and competent to participate according to the protocol, principles of Good Clinical Practice (GCP) and Declaration of Helsinki. If delegation of consent is undertaken then details should be recorded within the delegation log of the ISF.

A member of the research team will obtain informed consent prior to the undertaking any trial intervention. The exact timing for obtaining informed consent may vary between patients and will depend on the expediency of transplantation.

Wherever possible, patients will be provided with at least 24 hours to read the PIS, consider the information and ask questions. For patients recruited at time of transplant listing, this will be simple, and PIS will be sent out along with other routine information regarding transplantation prior to the clinic appointment, as is our standard practice. For patients recruited at the time of transplant admission, it can be more challenging to provide >24 hours of time for patients to consider participation within a research study, due to the expedient nature of transplantation. This is an issue that we commonly encounter consenting for trials for transplantation. Information regarding the trial will be placed on the unit's patient facing website and app so that interested patients will have access to the trial information prior to admission for transplantation. Beyond this, patients will be given as long as reasonably possible to consider their options and discuss them with research and clinical teams, acknowledging that a decision regarding participation must be made prior to transplantation (which in the case of deceased donor transplantation can happen in the middle of the night with <24 hours' notice). Patients will be encouraged to read the PIS fully consider the information provided, ask

questions and reflect as appropriate. However, the patient also has the right to make an immediate decision to consent.

All patients have the right to refuse participation without giving reasons. Participants remain free to withdraw from the trial at any time without giving reasons and without prejudicing his/her further treatment. If a patient declines to consent a record of this will be made within the patient notes and in the SCOPE study screening log.

Once signed, a copy of the consent form will be given to the patient; the original kept in the local ISF and a copy placed in the patient notes. The informed consent discussion will be recorded in the participant's medical notes including the version number of the PIS provided to the participant.

Patients recruited into the trial will be assigned a unique patient identifier allowing participant to be identified i.e. 001 on all future trial documentation. An enrolment log will be maintained in the ISF to permit identification of patient names against trial numbers for those recruited to the trial. The ISF will be retained at a secure location within the Renal Transplant Unit. The enrolment log is the only place where patient identifiable information will be recorded. Upkeep and security of the ISF is the responsibility of the PI.

Interventions/ trial procedures

The interventions within this study beyond standard care are the bladder diary, IPSS/ ICIQ-FLUTS questionnaire, a bladder scan (bedside ultrasound) to measure post-void residual volume and non-invasive uroflowmetry studies. These additional interventions will be performed at time of transplant listing (where appropriate), after 1 year on the transplant waiting list (where appropriate), on the day of transplant, 6 weeks and 12 months after transplantation.

A small number of patients will not pass sufficient urine to perform flow studies/ and or urodynamics. These patients will require their bladder to be pre-filled with sterile saline prior to voiding in order to achieve an accurate reading. A protocol for how to undertake this is outlined in Appendix 1 and would be performed by the ward doctor as part of clinical care. The rates of bladder filling and urodynamic studies being performed within trial will be monitored by the Trial Steering Committee at 3- 6 monthly intervals to ensure that these are clinically appropriate.

Study visits

A schedule of study visits is outlined below. All study visits will correspond to pre-existing clinical visits.

For patients recruited on day of transplant:

Study assessments	Visits			
	Screening visit	Enrollment visit (Day of transplant or day -1)	Week 6 +/- 2 weeks	Week 52 +/- 4 weeks
Assessment against eligibility criteria	X			
Provision of PIS	X			
Informed consent		X		
Demographics and past medical/urological history		X		
Bladder diary		X	X	X
IPSS/ICIQ		X	X	X
Bladder diary		X	X	X
Renal function		X	X	X
Uroflowmetry ⁺		X	X	X
Post-void residual ⁺		X	X	X
Urodynamics ⁺⁺		(X)	(X)	(X)
Urological complications			X	X
Other secondary outcome measures			X	X

For patients recruited in the transplant assessment clinic:

Study assessments	Visits					
	Screening visit	Enrollment visit (Transplant assessment)	1-year post-waiting listing*	Day of transplant or day -1)	Week 6 +/- 2 weeks	Week 52 +/- 4 weeks
Assessment against eligibility criteria	X					
Provision of PIS	X					
Informed consent		X		X		
Demographics and past medical/urological history		X	X	X		
Bladder diary		X	X	X	X	X
IPSS/ICIQ		X	X	X	X	X
Bladder diary		X	X	X	X	X
Renal function		X	X	X	X	X
Uroflowmetry*		X	X	X	X	X
Post-void residual*		X	X	X	X	X
Urological complications					X	X
Other secondary outcome measures					X	X

Data collection

Data will be collected from standardized data collection tools as outlined in section 7 and from within the Scottish Renal Electronic Record (SERPR).

Demographics, past medical and surgical history

Patient factors: Age, Gender, Ethnicity, BMI, Postcode

Relevant past medical history: Diabetes, Hypertension, Ischemic heart disease, cause of primary renal disease; RRT vintage; prior transplantation and duration of same; reason for prior graft loss if previous transplant

Past and present urological history: Any prior urological diagnosis/ interventions/ surgery; native urinary output; any prior urological assessment of bladder function/ volumes; LUTS symptoms (storage- frequency, urgency, nocturia, voiding- dribbling, struggling to initiate, incomplete emptying), caffeine and fluid intake, previous/ current use of catheters, previous urological surgeries, use of medications for LUTS (anticholinergics, 5-alfa reductase inhibitors, alfa agonists, intravesical Botulinum Toxin-A)

Transplant specific factors: Donor age, gender, any pre-existing/ known urological history in donor or anatomic irregularity with kidney e.g. duplex collecting system, dual transplant, horseshoe kidney, renal stones, renal cysts etc.), DBD/ DCD/ live donor, CIT, cRF, immunosuppressive regimen and induction agent, other relevant aspects of post-transplant course e.g. DGF, primary non-function, biopsy-proven rejection and treatment for same; documented operative complications with initial surgery

Bladder diary

We will be using the form prescribed by ICIQ (<https://iciq.net/iciq-bladder-diary>)

IPSS/ ICIQ-FLUTS

LUTS will be assessed by taking a complete urological history and using validated, gender appropriate questionnaires:

- Males: We will use the International Prostate Symptoms score (IPSS). Moderate to severe LUTS will be defined if the score is above 7¹⁵.
- Females: We will use the International Consultation on Incontinence Questionnaire – Female Lower Urinary Tract Symptoms (ICIQ-FLUTS). It does not have a total score, but instead measures the severity of following subscales separately:
 - Incontinence 0-20
 - Voiding 0-12
 - Filling 0-16

Whilst there is no official cutoff for severity for ICIQ-FLUTS, we aim to use the following cutoffs based on the published evidence¹⁷⁻¹⁹:

- Mild: total score 0–11
- Moderate: 12–23
- Severe: 24+

This stratification will ensure an accurate gender-specific assessment of baseline urinary symptoms and will allow the results to be meaningful, across subgroups having external validity.

Post-void residual bladder volume

This is a routine bedside test which uses a non-invasive ultrasound “bladder scanner” to measure how much urine is left in the bladder after a patient has urinated. The patient is asked to go to the bathroom to void urine and the urine void is captured and measured. Immediately following the urine void, a bladder scan of the residual (remaining) fluid levels within the bladder is made.

As some renal patients have been on dialysis for many years, there is a chance that a small number are anuric or do not make sufficient urine to make this scan reliable. In these situations (where the patient is able to pass less than 130ml at a single void), a cystoscopy (telescope test) will be performed to fill the bladder with fluid artificially and then the patient asked to void and the test repeated to ensure that an accurate result is obtained.

Uroflowmetry

This is a non-invasive test which measures the quality and strength of a patient’s urine flow and can help detect problems with the bladder outflow. While the patient is passing urine, the urine is captured within a jug on a scale, and this lets us assess “real-time” what is going on with the urine flow. Measurements such as Qmax (the maximal flow rate), time to fully empty the bladder, and the shape of the flow trace can be helpful in assessing the patient’s bladder outflow. This test would be conducted at that the same time and in the same manner as the urine voided for the post-void residual.

Occasionally, the urine flow is “non-diagnostic”. This can happen in cases where patients are anxious or the bladder is inadequately filled. If this is the case, the patient would be encouraged to drink some fluid and the study repeated +/- filling cystoscopy.

Invasive urodynamics (filling cystometry)

We do not intend on performing invasive urodynamics on every patient, only where clinically indicated. That clinical indication is likely to be detected elsewhere within the transplant work-up process (i.e. out with the study) but would include:

1. Diagnostic uncertainty persists despite the clinical history, questionnaires and non-invasive urodynamics.
2. Failure to provide a diagnostic uroflowmetry on two occasions despite using cystoscopy to fill the bladder
3. If initial transplant workup reveals a possibility of neurogenic lower urinary tract dysfunction (NLUTD).

If available as part of the clinical course, relevant invasive urodynamic data (bladder capacity, compliance, sphincter assessment, detrusor contractility, pressure-flow study, urodynamic diagnosis etc.) will also be captured.

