Furthermore, life expectancy advances have led an increase to the number of older people with ESRD undergoing RT. The UK Renal Registry consistently shows a trend towards increasing median ages for patients undergoing renal transplant. The median age of renal transplantation in men in UK was 46 years and 55 years in Scotland^{1,11}. In men

> 50 years of age, Lower urinary tract symptoms (LUTS) secondary to Bladder outlet obstruction (BOO) primarily caused by Benign Prostate Hypertrophy (BPH) linearly increases with age¹². LUTS generally present as symptoms related to urinary storage (increased urinary frequency, urgency, nocturia, incontinence) or urinary voiding (poor stream, hesitancy, incomplete emptying etc.). Symptoms of these relative common conditions can be masked in patients with renal failure due to oligo-anurisis. Urodynamic studies indicate that prolonged disuse of bladder may lead to structural and functional changes including reduced bladder compliance and impaired detrusor contractility⁹. LUTS can arise after RT leading to restoration of diuresis; potentially posing a serious risk to graft function¹³.

Several researchers have advocated for investigation and treatment of bladder function before RT owing to the high prevalence of these symptoms in pre-transplant patients. However, there is a paucity of prospective data linking LUTS with post RT urological complications and significant variability in practice within the UK and Europe regarding pre-operative evaluation of patients and no clear guidance on a standardized protocol^{5,13,14}.

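### The list of LUTS medicines to record names alpha-agonists, the wrong class, and omits alpha-blockers, so treatment that bears on male baseline scores may go unrecorded

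*Protocol*

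**What the plan says.** The Protocol describes the medication item once, in section 7 under demographics, past medical and surgical history. It asks for "use of medications for LUTS (anticholinergics, 5-alfa reductase inhibitors, alfa agonists, intravesical Botulinum Toxin-A". Four classes are named. The bracket contains no wording that marks the classes as examples, and no category for other medicines.

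The item sits in a wider paragraph that opens "Past and present urological history: Any prior urological diagnosis/ interventions/ surgery" and goes on to native urine output, earlier bladder assessments, storage and voiding symptoms, and catheter use. Under the IPSS/ICIQ-FLUTS heading of the same section, "LUTS will be assessed by taking a complete urological history and using validated, gender appropriate questionnaires". Male LUTS is classed as moderate to severe when the IPSS exceeds 7, with no reference to treatment.

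On men over 50, section 1 says that "Lower urinary tract symptoms (LUTS) secondary to Bladder outlet obstruction (BOO) primarily caused by Benign Prostate Hypertrophy (BPH) linearly increases with age". Section 8 says that "Data analysis will be exploratory with the primary aims of describing the distribution of LUTS scores for males and females". It states no use of the medication item.

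**The concern.** The list is headed as treatments for LUTS, yet one of its four classes acts in the opposite direction at the bladder outlet from the alpha-class drugs used for outflow symptoms. That is general pharmacology and not something the Protocol states. The class one would expect beside 5-alpha reductase inhibitors, alpha-blockers, is missing from the whole document.

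What is at stake is whether treated men can be identified. The first primary objective is the distribution of LUTS scores, and a score taken on effective treatment means something different from the same score in an untreated man. If current alpha-blocker use is not captured, nobody can later describe the male distribution by treatment status from the medication field. That includes outside researchers who receive the archived dataset. Urinary retention is the first component of the complication composite, so treated outflow obstruction is relevant to the second primary objective as well.

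**Working it through.** No arithmetic applies: the item rests on no sample size, rate or effect figure. The check compares the relevant places in the Protocol.

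1. **Is the class wrong, or only misspelt?** The spelling *alfa* is used consistently in the list and is harmless. The word *agonists* is the problem. The adjacent 5-alpha reductase inhibitors make alpha-antagonists the likely intention. This is an inference. Beta-agonists are also absent from the list, and the text alone cannot exclude that they were meant. On either reading, alpha-blockers have no named place.

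2. **Is the class named elsewhere?** No. Neither alpha-blockers nor alpha-antagonists appear anywhere in the Protocol.

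3. **Is the list closed?** It reads that way. Other lists in section 7, such as the donor anatomy items and the urodynamic measures, are marked as examples or left open-ended, and this one is not. The data go into a spreadsheet (section 8), and four columns would be a natural transcription. The data form itself is not shown, so whether it copies the bracket is unknown.

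4. **Does the missing class matter to this population?** Section 1 describes symptoms from outlet obstruction as rising with age in men over 50 and gives a median transplant age of 55 years in Scotland. The passage names prostate enlargement as the main cause of the obstruction. It does not rank obstruction among the causes of LUTS, so it supports relevance but not a claim about how many men are affected.

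5. **How often is the item collected?** For patients recruited on the day of transplant, the visit table in section 7 ticks the history row at enrolment only. The consent text says a deceased-donor transplant can come at night with less than 24 hours' notice. For patients recruited at wait-listing, the row is repeated at one year on the list and at transplant, so an omission there has further chances of being noticed.

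6. **What else would identify a treated man?** Prior diagnoses and interventions, the urological history, uroflowmetry and post-void residual are all recorded at baseline. A diagnosis does not show whether a drug was being taken when the IPSS was completed. Flow and residual are themselves measured on whatever treatment the man is taking. These items would find some treated men, but not reliably all.

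7. **Would correcting the word change how scores are read?** Not by itself. The cut-off of 7 applies whatever the treatment, and section 8 states no analysis by medication. Recording the class correctly makes a description by treatment status possible but does not carry it out.

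**The case against.** The best counter-argument is that this is an evident slip with little practical effect. The item asks generally for LUTS medication, and the bracket may only illustrate it. The study is run jointly with a urology department, whose staff would probably recognise the error. The diagnosis, history, flow and residual data remain. Analysis by medication could properly sit in a statistical analysis plan that is not shown. Most of this stands, and it keeps the point minor. It does not remove the point, because an analysis plan cannot use a variable that the form never held. Nor does the Protocol say that a urologist takes the history on the night of transplant.

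A reader might go further and infer that men on alpha-blockers are recorded as untreated and their lowered scores counted as naturally mild LUTS, which dilutes any link between LUTS and complications. The documents do not support this. Nothing directs that such men be coded as untreated. A man scoring 7 or below on treatment falls in the low group whichever class the list names, so any dilution comes from scoring men on treatment and not from the wording. Putting a figure on it would need the prevalence of alpha-blocker use, the share of users scoring low, and their complication risk. The Protocol gives none of these. The objective on pre-existing urological conditions is not shown to suffer either, because prior diagnoses are recorded directly.

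**Conclusion.** The error in the text is certain: the list names the wrong class for LUTS treatment, and alpha-blockers appear nowhere. The consequence is a risk. It depends on the data form copying the list literally as a closed set. In that case alpha-blocker use may be missed, and the medication field would not separate on-treatment from untreated IPSS scores, although other recorded data would identify some of these men. The size of the effect cannot be derived from the documents. This is a minor data-capture correction that leaves the study design as it is.

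**What to change.** In the medication list in Protocol section 7 and on the data form:

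- replace *alfa agonists* with alpha-blockers (alpha-1 antagonists);
- add a free-text field for other LUTS medication (specify), which would also capture beta-3 agonists and settle the doubt about which class was meant;
- in the protocol or the analysis plan, state that the baseline LUTS distribution will be described with patients on LUTS medication identified.

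The third step is needed because the first two only make the information available. The cost is a one-line protocol edit, one extra form field and one descriptive breakdown. No visit, test or treatment changes. It is cheapest before recruitment starts, because current drug use on the day of transplant is harder to recover afterwards.
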